Screening visit(s). Screening procedures may be scheduled across more than 1 day to meet participant schedules. Prior to completing any study-related screening, participants will review and sign an informed consent form with a trained staff member. Participants will be given the opportunity to do an in-person or a remote consent. For participants that complete the remote consent, some screening procedures will also be completed remotely, including interviews and questionnaires. Participants who complete this initial eligibility screening will complete the remainder of their screening visit in person. During the screening visit, participants will be assessed for inclusion and exclusion criteria. A urine drug-screen will be collected to assess for recent drug exposure and pregnancy (when indicated), the Mini-International Neuropsychiatric Interview (M.I.N.I.), the Addiction Severity Index (McLellan, Cacciola, & Zanis, 1997), the Columbia Suicide Severity Rating Scale, a demographic questionnaire, and a health form assessing current conditions and medications will be used to help evaluate participant eligibility.

Baseline/Randomization visit. Following determination of eligibility, participants will be randomized (stratified by gender) to receive 20mg of SUVO (the maximum FDA approved dose) or placebo. Randomization will occur prior to visit 1. At the randomization visit, participants will provide a urine sample that will be tested for recent drug use and complete self-report measures as described below. They may also complete a cue-induced craving paradigm, a probabilistic reward task, and the Trier Social Stress Test (TSST) described below. Participants will also be provided with an actigraph-like device to wear for the duration of their study participation to assess sleep.

Medication dispensing will begin during the baseline session. Participants will receive a blister package with 7-days of medication dispensed as two capsules (10mg SUVO or placebo) so that medication doses can be reduced to 50% of the dose if requested by a

Date: 09/19/2024

Principal Investigator: [name].

Application Number: IRB00341328

participant. Participants will also receive a 3-day blister package as a contingency strategy in case of missed visits. Participants will be instructed to return blister packages once weekly as a measure of medication compliance.

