Weekly visits. Participants will complete visits twice weekly during the study period. At these visits, participants will be asked to complete a urine drug screen and self-report measures as described below. Medication will be dispensed once weekly during these visits.

Final/Exit visit. The final study visit will be collected at day 28-30 (+7 days) or the final day of study participation. At their final visit, participants will complete a urine drug screen and self-report measures, and tasks. Participants will be able to request SUVO prescriptions from their provider if desired and all participants can request study drug unblinding after data collection is closed.

Follow-up phone visit: Participants will be contacted via phone after the final/exit visit. Information will be collected on their experience during the study, any changes in symptoms following study exit, treatment plans going forward, and other feedback regarding the study.

Sleep diaries: To facilitate scoring of actigraphy data, participants will be asked to complete nightly sleep diaries.

The following study Measures may be used:

- Mini-International Neuropsychiatric Interview (M.I.N.I.): The MINI is a semi-structured interview that will be used to assess presence of stimulant use disorder.
- Addiction Severity Index: The ASI will be used to collect information related to severity of recent substance use disorder
- Columbia Suicide Severity Rating Scale: The C-SSRS is the standard for assessing present risk for suicidality. It will be administered at screening and end of study, and point prevalence during the study as indicated.
- Demographic questionnaire. This will ask participants basic demographic information (e.g., gender, age, race, ethnicity, employment status, etc.)
- Medical History: A self-reported medical history will be collected to determine eligibility for suvorexant administration.
- Assessment of previous medication administration: Participants will be asked whether they have ever received a number of different medications, either illicitly or through a prescription.
- Medication expectancy questionnaire. Participants will be asked to rate how much they expect to like the study drug, as well as how much they expect the study drug to help improve various symptoms (i.e., opioid use, cocaine use, sleep, stress).

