- Hypothetical purchase tasks: Participants will complete several questions asking how much they would purchase of various substances at various prices.
- Hypothetical Monetary Choice: Participants will ask whether they would hypothetically prefer a smaller amount of money at a shorter time interval, or a larger amount of money after a delay.
- Blood pressure, heart rate, and weight
- Opioid/cocaine cued choice: A paradigm in which participants will be shown two images (cues: one cocaine or opioid and one control image) presented side-by-side followed by concurrent monetary offers below each image.
- Time since last methadone or buprenorphine dose.
- Time Line Follow Back: Participants will be asked to identify “anchor events” in the time period assessed, and will then be prompted to report on their substance use, using anchor events as a guide.
- Urine Drug Screen: Qualitative tests will be used to assess evidence of recent exposure to illicit substances such as opioids, cocaine, methamphetamine, benzodiazepines, fentanyl, and cannabis. Tests will also confirm presence of buprenorphine or methadone.
- STOP-BANG questionnaire will be used as a screening measure for sleep apnea.

Date: 09/19/2024

Principal Investigator: [name].

Application Number: IRB00341328

b. If your study involves data/biospecimens from participants enrolled under other research studies with a written consent or under a waiver of consent, please list the IRB application numbers for those studies. Please note: Certificate of Confidentiality (CoC) protections applied to the data in source studies funded by NIH or CDC will extend to this new study if the funding was active in 2016. If this situation applies, Section 36, question 6 in the application will need to be answered “Yes” and “Hopkins Faculty” should be selected in question 7. No other documents are required.

N/A

c. Study duration and number of study visits required of research participants.

Participants will complete 9-10 visits (10 visits if a screening visit is broken into two visits for participant convenience) across a period of approximately 5-6 weeks: a screening visit(s), a baseline/randomization visit and 8 twice weekly visits between the 28-30 days of SUVO administration. The estimated study duration is 1 year.

d. Blinding, including justification for blinding or not blinding the trial, if applicable.

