Suvorexant is a Schedule IV dual orexin receptor antagonist (DORA) that is FDA-approved for the treatment of insomnia. Suvorexant is 82% bioavailable and has a Tmax of 2 hours. Tmax can be delayed by food though this does not impact the Cmax. It is extensively metabolized by the liver through CYP3A enzymes. The elimination half-life is 12 hours, and it is excreted through both renal (23% unchanged) and fecal (66%) means. Suvorexant is contraindicated with other CNS depressants and alcohol and strong CYP3A inhibitors. It is rated pregnancy category C, indicating insufficient data available to make determination for human subjects. Suvorexant is contraindicated in patients with narcolepsy, patients with recent suicidal behavior, or patients with severe hepatic impairment. There is no evidence of potential overdose and a toxic dose has not been established. Clinical trials that administered up to 240mg of suvorexant reported no overdose effects, though there was a dose-dependent increase in the frequency and duration of next day somnolence. As per product label, most common side effects are sleepiness/drowsiness (7% of people), headache (7%), dizziness (3%), diarrhea (2%), dry mouth (2%), upper respiratory infection (2%), abnormal dreams (2%), and cough (2%). Serious adverse effects include sleep paralysis (7%), somnolence (7%), and worsening of depression or suicidal ideation.

b. Steps taken to minimize the risks.

Individuals with medical or psychiatric contraindications and/or individuals who are taking exclusionary medications (including CNS depressants such as benzodiazepines or other sleep medications), individuals with co-occurring moderate or severe substance use disorder, those with current and major psychiatric illness (e.g., bipolar disorder) or past 30-day suicidal behaviors are excluded for participating. Participants will be provided the maximum FDA-approved dose (20mg). All medication will be dispensed in two (10mg) capsules and participants will be informed they can refuse reduce from 2 to 1 capsule or stop taking medication at any point and we will track participant acceptance (e.g., in terms of adherence with dosing schedule) of the medication as part of the study. Given that suvorexant can cause next-day drowsiness, participants will be explicitly instructed not to drive or operate heavy machinery under any circumstances within 8 hours of taking suvorexant for the first time, or if they continue to feel

Date: 09/19/2024

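### Suicidal ideation is a listed serious effect of the study drug, yet no C-SSRS rating is scheduled between first dose and end of study, a gap of about 28-30 days that existing dispensing visits could close cheaply

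*Combined protocol and SAP*

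**What the plan says.** **The risk.** Section 8a (medical risks): "Serious adverse effects include sleep paralysis (7%), somnolence (7%), and worsening of depression or suicidal ideation". No frequency is attached to ideation.

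**The instrument.** Section 4a presents the C-SSRS as the reference tool for current suicide risk and sets its timing: "It will be administered at screening and end of study, and point prevalence during the study as indicated". No section defines the indication. The measures list is introduced permissively, as measures that may be used. The screening visit does include the scale for eligibility, alongside other forms ("the Columbia Suicide Severity Rating Scale, a demographic questionnaire, and a health form assessing current conditions and medications").

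**Dispensing.** Section 4a: "Medication dispensing will begin during the baseline session", with a 7-day pack of two 10 mg capsules per night. "Participants will also receive a 3-day blister package as a contingency strategy in case of missed visits". After that, "Medication will be dispensed once weekly during these visits". The final visit is at day 28-30, with a further 7 days allowed, or on the last day of participation.

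**Visits.** Section 4c gives "8 twice weekly visits between the 28-30 days of SUVO administration" and places the whole course, screening included, "across a period of approximately 5-6 weeks".

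**Other safeguards.**
- Adverse events and serious adverse events are assessed at each visit, and participants have a contact number (Sections 7b, 8b).
- The PANAS is given at weekly visits (Section 4a).
- Events go to the study physician daily, and some prompt an immediate call to the medical team (Section 8b).
- Treatment for opioid use disorder continues throughout (Section 4e), and the medical team can withdraw anyone for whom continuing is unsafe (Section 4g).
- Suicidal behavior in the 30 days before entry is an exclusion (Section 5), as is current major psychiatric illness (Section 8b).

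**The concern.** The protocol identifies a psychiatric risk of the drug, has a purpose-built instrument for it, and sees participants twice a week. Yet the instrument is fixed only before the drug starts and at the end of the study. Ideation that arises during dosing would be picked up by schedule only at the last visit, after the weekly packs have been handed out. Before then, detection depends on a participant volunteering it, on an adverse event enquiry whose content is not described, or on staff judging that a rating is indicated without a stated rule.

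What is at stake is participant safety in a take-home regimen at the maximum approved dose. The efficacy analysis is not touched.

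**Working it through.** There is no planned figure to reproduce. The check is a comparison of the schedule with the dosing period, followed by a cost count.

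**Inputs from the protocol:** 28-30 days of dosing; final visit at day 28-30 plus up to 7 days; 8 visits on treatment; 7-day packs plus one 3-day pack; whole course about 5-6 weeks; 40 participants.

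**Assumptions:** refills at about days 7, 14 and 21, possibly also day 28; 3-10 minutes per rating; the final visit is the last of the 8 on-treatment visits.

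**1. Time on study without a scheduled rating.**
- First dose to next fixed C-SSRS: 28-30 days. With the window, the latest is 30 + 7 = 37 days.
- Four packs and the contingency pack supply 4 × 7 + 3 = 31 days, so on that supply the last part of a 37-day gap would be off drug.
- Of the 8 on-treatment visits, 1 has a fixed C-SSRS and 7 have none.
- A participant who leaves without an exit visit has none after the first dose.

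**2. Age of the screening rating at first dispensing.** If the final visit falls at the end of dosing, the gap is 5 × 7 − 30 = 5 days to 6 × 7 − 28 = 14 days. This is only a rough range, because it is obtained by subtraction from an approximate course length.

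**3. Do the other checks ask about ideation?**
- *Adverse event assessment at each visit:* the content of the enquiry is not described. The form fields listed in Section 8b concern how an event is recorded.
- *PANAS, Perceived Stress Scale, GAD-7:* described as measures of affect, stress and anxiety. No depression scale is listed.
- *Escalation:* it acts on events already detected. The triggers are an a priori threshold (not given), an unexpected event or severity, or the participant's own concern. Ideation is a listed effect, so it may not count as unexpected.
- *Entry exclusions:* Section 5 names behavior and not ideation, and no entry screen can detect what arises later.
- *Follow-up call:* it covers changes in symptoms, but no ideation measure is named.

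**4. Schedule with a rating at each dispensing.** The longest scheduled interval on drug becomes about 7 days, or 7 + 3 = 10 if the contingency pack covers a missed visit.

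**5. Cost.**
- Ratings per participant: 1 + 3 = 4, or 1 + 4 = 5 with a day-28 refill.
- Total: 40 × 4 = 160 to 40 × 5 = 200.
- Staff time: 160 × 3 / 60 = 8 hours to 200 × 10 / 60 = 33.3 hours.
- Per participant: 4 × 3 = 12 minutes to 5 × 10 = 50 minutes.

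**The case against.** The best defense is that the documents show only that an ideation question is not stated. The standardized adverse event form and the safety thresholds are not reproduced, and either could contain the question or the trigger. The C-SSRS may already be used between the fixed points, staff see participants twice a week, and ideation as a listed effect falls within adverse event assessment. On this view the rest is a preference about frequency, which one sentence defining the trigger, or stating that the enquiry covers mood and ideation, would meet.

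Much of this stands. The gap is one of scheduling and specification, and if the form already asks about ideation, saying so would close part of it. But a rule in an unseen form is not one a reader of the protocol can rely on, and a defined trigger still works only after something has raised suspicion. A short scheduled question does not depend on that.

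Two further objections also stand. The word serious in Section 8a is used loosely: somnolence appears there at 7%, after drowsiness has been listed as a common side effect at the same rate. And probing for ideation changes how adverse events are ascertained, which matters because their number is compared between arms by t-test under Secondary Aim 2 (Section 7c). That effect applies equally to both blinded arms, but counts could differ between participants seen before and after a change.

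**Conclusion.** The concern holds as a narrow safety-schedule gap: about 28-30 days, and at most 37, from first dose to the next scheduled ideation rating, with no stated trigger in between. It is a cheap improvement. The size rests on the protocol's own dosing days and visit window; refill days and minutes per rating are assumptions. The documents give no ideation frequency, so the number of cases that would be found earlier cannot be estimated.

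Three stronger readings are not supported:
- *That suicidality goes unmonitored.* Adverse event checks, escalation, as-indicated C-SSRS use and continuing clinical care are all in the plan.
- *That participants go 35-42 days on drug without a rating.* The 5-6 week course includes time before the first dose.
- *That a week's supply is itself an overdose hazard.* Seven nights is 7 × 20 = 140 mg, or 200 mg with the 3-day pack. Section 8a reports no overdose effects in trials of up to 240 mg, though it does not address combination with opioids. The case for asking at dispensing is that it is a fixed weekly contact.

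**What to change.** In the C-SSRS entry of Section 4a, replace the as-indicated clause with a schedule: *a brief C-SSRS covering the time since last contact, completed before medication is dispensed at baseline and at each weekly dispensing visit, and additionally as indicated.* Keep the screening rating and the final or early-exit rating.

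Send new or worsened ideation or behavior through the existing escalation route in Section 8b, with the clinical response left to the study physician. Ideation already present at screening is noted but is not a new event. Report events elicited by the C-SSRS separately from the Secondary Aim 2 count, or flag them, so that counts stay comparable with any participants already enrolled.

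The cost is 160-200 short ratings at existing visits (8-33 staff hours on the stated assumption), a minor protocol amendment, and slightly more intensive adverse event ascertainment in both arms. No new visit is needed, and the scale is already in the protocol.
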